- **Process for Aim 1e:** Measure the patient-level change in rate of hypoglycemic events as the patient-level slope of the six-month linear change in the so-called “intensity” (λ) of the estimated nonhomogeneous Poisson point process. Once we’ve computed each patient’s six-month linear change in λ , we will compare the distributions between randomized groups. Note that the motivation for measuring change in frequency as the slope of λ estimated from a non-homogeneous Poisson process is that it allows us to compare changes in frequency of hypoglycemic events between groups with different modes of monitoring (continuous vs daily).

Aim 2: Assess impact of CGM on healthcare utilization and cost

Specific Aim 2a: Measure the effect of CGM vs. standard finger-prick protocol on healthcare utilization

- **Hypothesis for Aim 2a:** The count of primary care, specialist, and emergency department visits or hospital stays over six months will be fewer among those randomized to CGM than that among those randomized to standard finger-prick protocol.
- **Process for Aim 2a:** For each patient, count their visits to a primary care provider or specialist or emergency department/hospital admission. Next, compare the distributions of visit counts between randomized groups using a Poisson test, aggregated as well as stratified by visit type. Other metrics for evaluating utilization may include: current HEDIS performance on diabetes and behavioral health measures, coding specificity for diabetes, emergency department visit per 1000 rate, overall and for patients with diabetes, and hospitalization per 1000 rate related to diabetes.

Specific Aim 2b: Measure the effect of CGM vs standard finger-prick protocol on cost

- **Hypothesis for Aim 2b:** The total variable cost associated with healthcare services/visits over six months will be fewer among those randomized to CGM than that among those randomized to standard fingerprick protocol.
- **Process for Aim 2b:** For each patient, measure total variable cost of associated healthcare services and visits. Then compare the distribution of costs between randomized groups using the Wilcoxon rank-sum test, a non-parametric analogue of Student’s *t*-test.

Aim 3: Qualitatively understand patient perspective of CGM

Specific Aim 3a: Record patients’ self-reported willingness to participate in a CGM pilot

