4.2 Methods

Patients will be screened for eligibility per Inclusion and Exclusion criteria (See Sections 3.3.1 and 3.3.2 respectively) and consented as described in Section 4.1.

The following information will be obtained from each subject's medical records, and/or during procedures, treatments, study-specific visits, and/or follow-up visits that are generally part of their usual or specialized care:

- Patient's ID number (EMPI)
- General demographic information (age, gender, height, weight, race, ethnicity)
- Patient's contact information (email, home address, and phone)
- Health history (personal health history, previous laboratory and glucose test results, medications, healthcare utilization and cost data)
- Current medications/medication history
- Glucose levels and historical A1c reports

Group #2 data will be transmitted from the Contour Next One device to the Contour mobile app via Bluetooth. Should this process fail, a contingency plan has been devised for patients to manually record their readings in an online REDCap form or provide their readings to their Research Coordinator who will properly store the data. Patients in the intervention group will have their data automatically uploaded via the Dexcom G6 app where it will then be obtained by Intermountain Healthcare researchers. No protected health information will be shared with those outside of this research study unless approved by the IRB. Coordinators will check in with the patients on a monthly basis (or more frequently for non-compliance) to ensure proper data entry and to answer any questions (if necessary).

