7.1 Statistical Considerations

The primary analysis (Aim 1a) will measure the intervention effect on the patient-level six-month absolute reduction in mean HbA1c. Since not all patients will have their final HbA1c test at six months exactly, we will estimate each patient's six-month reduction in HbA1c by interpolating/extrapolating from their assessments, given that their HbA1c levels were assessed on at least two occasions: baseline, and >3 months post baseline. Then, among patients with a sufficient number of occasions of HbA1c assessments, we will estimate their sixmonth HbA1c using generalized linear mixed models with patient-level random slopes and intercepts, with appropriate link function and distributional family [8]. The quantitative secondary analyses (Aims 1b-e, 2a-b) will use outcomes related to the longitudinal change in various metrics of glycemic variability (MAGE, C_v , range) as well as the frequency of hypoglycemic events, healthcare utilization, and cost. The secondary analyses will also use longitudinal data analysis to assess whether there is a significant reduction in glycemic variability over six months (Aims 1b-d) among those randomized to CGM, whether there is a significant reduction in hypoglycemic events over six months (Aim 1e) among those randomized to CGM, and to assess whether overall healthcare utilization and costs differ between randomized groups [9]. Accordingly, specific aims 1b-e will rely heavily on longitudinal data analysis within a multilevel/hierarchical framework [10], specifically using generalized linear mixed models. In the sensitivity analyses, provider variability will be accounted for using three-level (provider, patient, occasion), quasi-Bayesian generalized linear mixed models [11]. Finally, the sensitivity analyses exploring HTE will use generalized additive models (GAM) to identify subgroups of patients for whom CGM is likely to have a differential effect [12-13].

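### Aims 2a and 2b compare six-month visits and cost without adjusting for prior utilization and cost, which loses precision, and the plain Poisson test understates error if visit counts are overdispersed

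*Combined protocol and SAP*

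**What the plan says.** **Aim 2a (Section 2.0).** The hypothesis is that "The count of primary care, specialist, and emergency department visits or hospital stays over six months will be fewer" in the CGM arm. The process is to "compare the distributions of visit counts between randomized groups using a Poisson test", both overall and separately for each type of visit. No covariate is named.

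**Aim 2b (Section 2.0).** The plan is to "compare the distribution of costs between randomized groups using the Wilcoxon rank-sum test". Again no covariate is named.

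**Data source (Section 4.2).** The items taken from medical records or from visits include "Health history (personal health history, previous laboratory and glucose test results, medications, healthcare utilization and cost data". No look-back window is given.

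**Randomization (Section 3.0).** Assignment uses a random number list and envelopes. No stratification is described.

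**Analysis sections (7.0 and 7.1).** Section 7.1 says the secondary analyses will use longitudinal data analysis, among other things "to assess whether overall healthcare utilization and costs differ between randomized groups". It then states that "specific aims 1b-e will rely heavily on longitudinal data analysis within a multilevel/hierarchical framework", which leaves out Aims 2a and 2b. The exploratory sensitivity analyses cover heterogeneity of treatment effect and providers: "provider variability will be accounted for using three-level (provider, patient, occasion), quasi-Bayesian generalized linear mixed models". None of this names prior utilization or cost as a covariate.

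**The concern.** Visit counts and cost usually differ widely between patients, and heavy users often remain heavy users. Section 1.1 describes these clinics' patients as having four comorbidities on average. If prior use predicts later use, a test on follow-up values alone leaves explainable variation in the error term and does nothing about chance imbalance in prior use. With about 100 patients analyzed, that matters for the aims on utilization and cost, which Section 1.1 treats as critical before more clinics are opened.

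Aim 2a has a second problem. A plain Poisson test takes the variance of the counts to equal their mean. If patients' underlying visit rates differ, the variance is larger, the standard error is too small, and the test rejects too often when there is no effect. That affects validity, not only efficiency.

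**Working it through.** **1. The plan's own figure.** Section 7.2 enrolls 125, expects 20% attrition and analyzes 100: 100/(1 − 0.20) = 125. With 50 per arm and two-sided alpha 0.05 (both assumed; the documents state neither allocation ratio nor alpha), power at d = 1/1.25 = 0.8 is 97.9%. The claim of more than 80% is therefore true. It concerns HbA1c only; no power, event rate or SD is stated for Aims 2a or 2b.

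**2. Gain from adjustment.** Let rho be the correlation between prior and follow-up values, assumed over a range. Adjustment multiplies error variance by 1 − rho² and interval width by √(1 − rho²). The equivalent unadjusted sample is 100/(1 − rho²).

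| rho | Variance factor | Width factor | Equivalent N | Detectable d, 80% power | Power at d = 0.4 |
|---|---|---|---|---|---|
| none | 1 | 1 | 100 | 0.56 | 52% |
| 0.3 | 0.91 | 0.95 | 110 | 0.53 | 55% |
| 0.5 | 0.75 | 0.87 | 133 | 0.49 | 64% |
| 0.7 | 0.51 | 0.71 | 196 | 0.40 | 80% |

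**3. What rho might be for counts.** For gamma-Poisson counts with mean m in each period, relative rate variance v and persistence p (the correlation of a patient's underlying rates in the two periods), rho = p·m²v/(m + m²v). All inputs are assumed.
- m = 4, v = 0.3, p = 0.5: 0.5 × 4.8/8.8 = 0.27; equivalent N = 108.
- m = 4, v = 1.0, p = 0.8: 0.8 × 16/20 = 0.64; equivalent N = 169.
- Rare visit type, m = 0.2, v = 1.0: p × 0.04/0.24 gives 0.08 (p = 0.5) to 0.13 (p = 0.8); equivalent N = 101 to 102.

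**4. Simulation, Aim 2a.** Settings: 50 per arm, mean 4 visits in six months, rate ratio 0.7, 400 replicates, robust-error Poisson regression with and without log(1 + prior count). The simulated prior period was twelve months with mean 8, so results are best read by realized correlation.
- The standard error fell 3–4% at correlation about 0.24, 7–8% at 0.35, 13% at 0.46, about 30% at 0.7 and about 45% at 0.8.
- Power went from 30% to 31% at the weakest correlation and from 42% to 83% at the strongest.
- Under no effect, the adjusted robust test rejected 5.75–8.0% of the time, against a simulation error of about √(0.05 × 0.95/400) = 1.1 points. It can therefore run slightly liberal at this size, which flatters the adjusted power a little.

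**5. Overdispersion.** The variance-to-mean ratio is 1 + mv. At m = 4 it is 2.2 for v = 0.3 and 5 for v = 1.0. A nominal 5% Poisson test then has an effective cutoff of 1.96/√2.2 = 1.32 or 1.96/√5 = 0.88, giving false-positive rates of about 19% and 38%. The simulated null scenarios, with larger rate variance at the top end, gave 21–50%.

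**6. Simulation, Aim 2b.** Settings: log-normal cost, shift of 0.4 SD on the log scale, 2,000 replicates. Wilcoxon power was 46–50%. Rank ANCOVA on prior cost gave 50%, 59% and 74% at rho 0.3, 0.5 and 0.7. Type I error was 4–5% for both.

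**The case against.** The strongest reply is that lack of adjustment is a choice, not an error. Randomization keeps both comparisons unbiased, these are secondary aims of a self-described pilot, and the plan claims no power for them. This stands, and it limits the point to precision, apart from the Poisson variance.

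The size of the gain rests on inputs that the documents do not contain. Four comorbidities show burden, not persistence of use. At rho = 0.3 the interval narrows by only about 5%, and for rare visit types almost nothing is gained. This also stands.

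A reader might infer from Section 4.2 that a pre-enrollment extract is already planned, so that adjustment needs no further data work. The text does not establish that. The word for earlier data directly qualifies only the laboratory and glucose results, the list also covers data from follow-up visits, and no window is set. The health-history label supports the reading but does not settle it.

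A reader might also infer that a few very costly patients could decide Aim 2b. Ranks limit the pull of extreme costs, so that argument is weak for the Wilcoxon test. It has more force for summed visit counts.

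Finally, Section 7.1 mentions longitudinal analysis for utilization and cost, and Section 7.0 extends the sensitivity models to each quantitative aim. Patient-level random effects there could absorb some overdispersion. But those analyses are exploratory, name no prior-period covariate, and do not replace the tests in Section 2.0.

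**Conclusion.** The point holds as a matter of precision for Aims 2a and 2b, with a validity element for Aim 2a. The planned tests use no prior utilization or cost, and no other section supplies that adjustment.

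The error variance that adjustment would remove is about 9%, 25% or 51% at a correlation of 0.3, 0.5 or 0.7. The gain is small below about 0.3, material from about 0.5, and negligible for rare visit types such as hospital stays. These figures assume 50 per arm and a correlation that the documents do not give.

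If counts are overdispersed, which is likely but not shown in the documents, the plain Poisson test would give false-positive rates well above 5%: about 19–38% by the formula under the assumed rates, and 21–50% in simulation. A reader might conclude that the unadjusted comparisons are biased, or that the trial's main conclusion is at risk. Neither follows: treatment is randomized, and the primary HbA1c analysis is not touched.

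**What to change.** 1. **Section 4.2:** state a fixed six-month look-back before randomization for visits and for cost, the same for every patient.
2. **Aim 2a:** replace the Poisson test with negative binomial or robust-error Poisson regression on arm and log(1 + prior count), with an offset for follow-up time. The offset is needed because 20% attrition is expected and record access ends for patients who withdraw without agreeing to continued collection (Section 5.2). Because the robust test ran slightly liberal in simulation, name a small-sample correction.
3. **Aim 2b:** test with rank ANCOVA on prior cost. Rank ANCOVA gives no difference in mean cost, so estimate that separately from a named model with prior cost as covariate: a gamma GLM (if all costs are positive) or a linear model with robust errors.
4. **Sections 2.0 and 7.1:** reconcile the longitudinal wording for utilization and cost with the tests named under Aim 2.
5. **Timing:** prespecify all of this before any outcome is compared by arm, so that covariates are not chosen on results.

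The cost is SAP wording, one record query and a little analysis work, with no added patient burden. The downside is that the precision gain may be small if the correlation is below about 0.3; the overdispersion correction for Aim 2a is worth making regardless.

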Randomization will be assigned *a priori* using a random number generator from Microsoft Excel. Sub-Investigator will then transcribe these numbers and order them individually in concealed envelopes and present them to the Research Coordinators to ensure the CRC is blinded. At time of consent the Research Coordinator will hand the patient the earliest numbered envelope to randomize. . Patients in both randomized groups will be given the devices and one month supplies to ensure compliance with the protocol. The Study Coordinator and patient will exchange contact information so that the CRC may resupply the patient with necessary equipment at the end of their month supply. The CRC may meet the patient at their Reimagine Care Clinic or off site for patient convenience. All patients are expected to participate for six months, which is near the minimum duration sufficient to measure clinically meaningful changes in hemoglobin A1c related to gradual behavioral changes (e.g., diet, exercise, insulin administration). Further, each patient will complete 2 mandatory blood draws and one elective blood draw at their designated Reimagine Care Clinic to evaluate HbA1c level changes over the course of the study. Baseline HbA1c must be completed on day of enrollment (± 2 days) which Intermountain Healthcare may choose to cover if not paid for by patient's SOC. An elective blood draw will be considered for data if completed at 3 months (± 1 week) and a third required blood draw upon study completion (± 2 weeks) which the study may also choose to cover if not SOC. 2 weeks from 180 enrollment) which the study may pay for if not covered by patient's SOC. We postulate that those that have a more consistent interstitial glucose profile (which avoid the high peak to valley swings), will have a more pronounced difference in pre and post HbA1c levels. Specific Aim #1 above will help our team understand the relationship between interstitial glucose and HbA1c, along with other outcomes of interest which include weight loss, alterations in diet, change in physical activity, etc.

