7.0 STATISTICAL ANALYSIS

This study is a parallel randomized control trial that will evaluate the impact of CGM versus a standard fingerprick protocol, between and within randomized groups. The primary analysis (Specific Aim 1a) will measure the intervention effect on six-month change in HbA1c. The quantitative secondary analyses will measure the withinpatient longitudinal change in glycemic variability among CGM patients (Aims 1b-d) as well as the intervention effect on hypoglycemic events, healthcare utilization and cost (Aims 1e, 2a-b) between randomized groups. Additionally, for each of these aims, we will conduct exploratory sensitivity analyses: measuring provider variability and its effect, as well as looking at patient-level heterogeneity of treatment effect (HTE) to describe

subgroups of patients in whom the benefit of CGM might be amplified or attenuated. Technical details are provided in Section 7.1 *Statistical Considerations*.

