9.2 Compensation

Subjects will not receive any monetary or other forms of compensation for participating in this research study. Likewise, the investigators and their research staff will not receive any monetary or other forms of direct compensation for conducting this research study. Subjects who receive the Contour Next ONE will be asked to mail the device back to The Business Development Department at Intermountain Healthcare in a prepaid mailing envelope supplied to the patient upon study completion to ensure no compensating factors took part in the research study.

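### Aim 2b is titled as the effect of CGM on cost, but as written it supports only a statement about service and visit cost, with no mean difference or interval and study-supplied devices apparently uncounted

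*Combined protocol and SAP*

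**What the plan says.** Cost is a stated purpose in the synopsis and in the introduction to Section 2.0. Section 1.1 treats knowing the cost impact as critical before more clinic sites are added. The title of Aim 2b carries no restriction on what kind of cost is meant.

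The outcome beneath that title is narrower. The hypothesis concerns total variable cost of healthcare services and visits over six months, and the process says "For each patient, measure total variable cost of associated healthcare services and visits". The analysis is to "compare the distribution of costs between randomized groups using the Wilcoxon rank-sum test".

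Section 7.1 adds a general aim "to assess whether overall healthcare utilization and costs differ between randomized groups", under the heading of longitudinal analysis. Section 7.0 says "Additionally, for each of these aims, we will conduct exploratory sensitivity analyses: measuring provider variability and its effect", together with subgroup exploration. Neither section names a cost effect measure or an interval.

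On supplies, Section 3.0 says "Patients in both randomized groups will be given the devices and one month supplies to ensure compliance with the protocol", and that contact details are exchanged so that "the CRC may resupply the patient with necessary equipment at the end of their month supply". Section 9.2 adds that "Subjects who receive the Contour Next ONE will be asked to mail the device back". No section prices or counts these items. Section 4.2 lists "previous laboratory and glucose test results, medications, healthcare utilization and cost data" among the information taken from medical records or usual care.

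**The concern.** The arms differ in the monitoring device. A comparison of cost that may leave out the device and its consumables covers only part of what the title announces. Supplies handed over by a study coordinator need not appear in the care records from which cost data are drawn.

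There is also a gap in what is estimated. A leadership group deciding on expansion would want a dollar difference per patient and its uncertainty. A rank-sum p-value supplies neither, so there is no specified figure to set against a device cost. If savings on visits merely paid for the supplies, a correct result of lower visit cost could be quoted as lower cost overall.

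**Working it through.** **1. The plan's own figures.** There are none for Aim 2b: no cost effect, SD, power, device price, alpha or sidedness. The sample size reproduces: 125 × (1 − 0.20) = 100. I take 50 per arm; this assumes 1:1 allocation, which the text does not state.

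**2. Scope, side by side.** The title covers cost without limit. The hypothesis and process cover service and visit cost. The synopsis endpoint is cost of care. Devices and monthly supplies appear in Section 3.0 but in no cost definition. The last three statements are consistent with one another; only the title and the stated purpose are wider.

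**3. Assumptions for illustration.**
- Six-month control mean: either 16,752 / 2 = $8,376 or 9,601 / 2 ≈ $4,800. Both annual figures are national ones in Section 1.1 (all expenditure, and the part attributed to diabetes), not this system's variable cost.
- Lognormal costs, log SD 0.8 to 1.2, the same in both arms unless stated.
- Net supply cost D (CGM minus meter) over six months of $1,200 or $2,400.
- Two-sided rank-sum test at 0.05, 20,000 simulated trials per cell.

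**4. Visit saving exactly equal to D.** The CGM visit mean is base − D, so net cost is the same in both arms.

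| Base | D | D / base | Visit cost found lower under CGM |
|---|---|---|---|
| $8,376 | $1,200 | 14.3% | 9–15% |
| $8,376 | $2,400 | 28.7% | 27–53% |
| $4,800 | $1,200 | 25.0% | 21–41% |
| $4,800 | $2,400 | 50.0% | 79–99% |

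The range in each row runs from log SD 1.2 (low) to 0.8 (high). These are true positives for visit cost. The spread between bases shows that no single percentage describes this trial.

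**5. Rank result against mean result (50 per arm).**
- Equal means, log SD 1.2 v 1.0: the test favours the heavier-tailed arm in 15.9% of trials, against 2.3% per side when both log SDs are 1.0. That arm's median is exp(−(1.44 − 1.00)/2) = exp(−0.22) ≈ 0.80 of the other's, so the test is detecting a real shift in typical cost.
- Equal medians, means $4,800 v $3,766 (CV 1.5 v 1.0), a difference of 1,034 / 4,800 ≈ 22%: the test rejects in 5.2% of trials.

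The rank-sum result therefore cannot stand in for the mean difference in either direction.

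**6. Width of an interval for the mean difference.**
- $4,800 base, equal SDs: 1.96 × CV × 4,800 × √(2/50) ≈ $1,880, $2,820 and $3,760 at CV 1.0, 1.5 and 2.0.
- $8,376 base, difference in mean cost including supplies, simulated percentile bootstrap: median half-width about $2,500–4,400, coverage about 92–94%.

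Every half-width exceeds $1,200. On the $4,800 base at CV 1.0 it is below $2,400.

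**The case against.** The strongest reply is that the plan does not contradict itself. Hypothesis, process and synopsis endpoint all point to the cost of care delivered, and nobody following Aim 2b would compute the wrong quantity. That stands: the mismatch is with the title and the stated purpose.

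Three stronger readings are tempting, and the documents support none of them.

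- *The plan excludes device cost.* No section says so. Variable cost is undefined, as is which services count as associated, so exclusion is an inference from silence.
- *The rank-sum test is wrong.* It is valid for the distributional comparison that the aim describes, and the equal-means example shows it responding to a genuine difference in typical cost.
- *The trial cannot yield a mean or net cost.* Per-patient cost is to be measured, so means can be recovered. The study issues the supplies itself, so their cost could be added later if the units issued are recorded. The regression methods cited in Section 7.1 could also yield estimates. The gap is that none is specified.

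It is also fair that the benefit statements in the synopsis and Section 4.4 are hedged and promise no net-cost analysis, that the percentages above rest on assumed prices and bases, and that the added intervals will be wide. A wide interval is still informative: it shows readers that net cost is unsettled, which a p-value does not.

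**Conclusion.** The point holds as a minor one. The title and purpose of Aim 2b reach further than its outcome and analysis. Followed as written, it can say whether service and visit cost distributions differ. It specifies nothing that gives mean or net cost, which is the kind of information Section 1.1 wants before expansion.

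The textual finding needs no assumption beyond the labelled inference about devices. The size of the misreading risk cannot be fixed from the documents, because they give no price and no SD of cost. The simulated ranges depend on the assumed base, D and lognormal shape, and should not be quoted as properties of this trial. Aim 2b is secondary in a pilot, and the HbA1c conclusion and sample size are unaffected.

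**What to change.** In Aim 2b and Section 7.1, define two six-month outcomes per patient:

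- **A:** variable cost of healthcare services and visits, with variable cost defined.
- **B:** A plus study-supplied device and supply cost in both arms, as stated unit price × units issued, with one rule set in advance for returned Contour meters (credited, or costed for use only).

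Keep the planned rank-sum test on A. Beside it, report the difference in mean A and in mean B, each with a bootstrap 95% CI, and base any statement about total or net cost on B. If devices are not to be costed, retitle Aim 2b and limit its conclusion to service and visit cost excluding devices.

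The cost is a few lines of SAP text, a unit-price list, and a unit log kept at the resupply contacts already planned. The downsides are slightly low bootstrap coverage and intervals that will often leave net cost unsettled. Keeping the rank-sum test also protects power: for a 30% visit saving with 50 per arm it has about 57/40/30% at log SD 0.8/1.0/1.2, against 47/29/18% for a Welch comparison of means.
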